7.2.2 Reporting of Pregnancy and Lactation to the Sponsor-Investigator and to Merck

Although pregnancy and lactation are not considered adverse events, it is the responsibility of investigators or their designees to report any pregnancy or lactation in a subject (spontaneously reported to them), including the pregnancy of a male subject's female partner that occurs during the trial or within 90 days of completing the trial, or 30 days following cessation of treatment if the subject initiates new anticancer therapy, whichever is earlier. All subjects and female partners of male subjects who become pregnant must be followed to the completion/termination of the pregnancy. Pregnancy outcomes of spontaneous abortion, missed abortion, benign hydatidiform mole, blighted ovum, fetal death, intrauterine death, miscarriage and stillbirth must be reported as serious events (Important Medical Events). If the pregnancy continues to term, the outcome (health of infant) must also be reported.

Such events must be reported within 24 hours to the Sponsor-Investigator and within 2 working days to Merck Global Safety. (Attn: Worldwide Product Safety; [contact])

7.2.3 Immediate Reporting of Adverse Events to the Sponsor-Investigator and to Merck

7.2.3.1 Serious Adverse Events

A serious adverse event is any adverse event occurring at any dose or during any use of Merck’s product that:

- Results in death;
- Is life threatening;
- Results in persistent or significant disability/incapacity;
- Results in or prolongs an existing inpatient hospitalization;
- Is a congenital anomaly/birth defect;
- Is a new cancer (that is not a condition of the study);

- Is associated with an overdose;
- Is another important medical event

Refer to Table 6 for additional details regarding each of the above criteria.

Any serious adverse event, or follow up to a serious adverse event, including death due to any cause other than progression of the cancer under study that occurs to any subject from the time the consent is signed through 30 days following cessation of treatment, or the initiation of new anti-cancer therapy, whichever is earlier, whether or not related to Merck product, must be reported within 24 hours to the Sponsor-Investigator and within 2 working days to Merck Global Safety.

Non-serious Events of Clinical Interest will be forwarded to Merck Global Safety and will be handled in the same manner as SAEs.

Additionally, any serious adverse event, considered by an investigator who is a qualified physician to be related to Merck product that is brought to the attention of the investigator at any time outside of the time period specified in the previous paragraph also must be reported immediately to the Sponsor-Investigator and to Merck.

SAE reports and any other relevant safety information are to be forwarded to the Merck Global Safety [contact]

The Sponsor-Investigator will report significant new safety information associated with use of drugs in this trial (including serious, unexpected, suspected adverse reactions) to FDA in accordance with regulations under 21 CFR 312.32. Additionally investigators will submit a copy of these reports to Merck & Co., Inc. (Attn: Worldwide Product Safety; [contact]) at the time of submission to FDA.

All subjects with serious adverse events must be followed up for outcome.

7.2.3.2 Events of Clinical Interest

Selected non-serious and serious adverse events are also known as Events of Clinical Interest (ECI) and must be recorded as such on the Adverse Event case report forms/worksheets and reported within within 2 working days to Merck Global Safety. (Attn: Worldwide Product Safety; [contact]).

Events of clinical interest for this trial include:

1. an overdose of Merck product, as defined in Section 7.2.1 - Definition of an Overdose for This Protocol and Reporting of Overdose to the Sponsor-Investigator, that is not associated with clinical symptoms or abnormal laboratory results.
2. an elevated AST or ALT lab value that is greater than or equal to 3X the upper limit of normal and an elevated total bilirubin lab value that is greater than or equal to 2X the upper limit of normal and, at the same time, an alkaline phosphatase lab value that is less than 2X

the upper limit of normal, as determined by way of protocol-specified laboratory testing or unscheduled laboratory testing.*

*Note: These criteria are based upon available regulatory guidance documents. The purpose of the criteria is to specify a threshold of abnormal hepatic tests that may require an additional evaluation for an underlying etiology. The trial site guidance for assessment and follow up of these criteria can be found in the Investigator Trial File Binder (or equivalent).

7.2.4 Evaluating Adverse Events

The Sponsor-Investigator or a qualified designee will evaluate all adverse events according to the NCI Common Terminology for Adverse Events (CTCAE), version 4.0. Any adverse event which changes CTCAE grade over the course of a given episode will have each change of grade recorded on the adverse event case report forms/worksheets.

All adverse events regardless of CTCAE grade must also be evaluated for seriousness.

Table 6 Evaluating Adverse Events

An Sponsor-Investigator or qualified designee, will evaluate all adverse events as to:

V4.0 CTCAE Grading	Grade 1	Mild; asymptomatic or mild symptoms; clinical or diagnostic observations only; intervention not indicated.
	Grade 2	Moderate; minimal, local or noninvasive intervention indicated; limiting age-appropriate instrumental ADL.
	Grade 3	Severe or medically significant but not immediately life-threatening; hospitalization or prolongation or hospitalization indicated; disabling; limiting self-care ADL.
	Grade 4	Life threatening consequences; urgent intervention indicated.
	Grade 5	Death related to AE
Seriousness	A serious adverse event is any adverse event occurring at any dose or during any use of Merck product that:	
	† Results in death ; or	
	† Is life threatening ; or places the subject, in the view of the investigator, at immediate risk of death from the event as it occurred (Note: This does not include an adverse event that, had it occurred in a more severe form, might have caused death.); or	
	† Results in a persistent or significant disability/incapacity (substantial disruption of one's ability to conduct normal life functions); or	
	† Results in or prolongs an existing inpatient hospitalization (hospitalization is defined as an inpatient admission, regardless of length of stay, even if the hospitalization is a precautionary measure for continued observation. (Note: Hospitalization [including hospitalization for an elective procedure] for a preexisting condition which has not worsened does not constitute a serious adverse event.); or	
	† Is a congenital anomaly/birth defect (in offspring of subject taking the product regardless of time to diagnosis);or	
	Is a new cancer ; (that is not a condition of the study) or	
	Is an overdose (whether accidental or intentional). Any adverse event associated with an overdose is considered a serious adverse event. An overdose that is not associated with an adverse event is considered a non-serious event of clinical interest and must be reported within 24 hours.	
Other important medical events that may not result in death, not be life threatening, or not require hospitalization may be considered a serious adverse event when, based upon appropriate medical judgment, the event may		

	jeopardize the subject and may require medical or surgical intervention to prevent one of the outcomes listed previously (designated above by a †).	
Duration	Record the start and stop dates of the adverse event. If less than 1 day, indicate the appropriate length of time and units	
Action taken	Did the adverse event cause the Merck product to be discontinued?	
Relationship to test drug	
Did the Merck product cause the adverse event? The determination of the likelihood that the Merck product caused the adverse event will be provided by an investigator who is a qualified physician. The investigator's signed/dated initials on the source document or worksheet that supports the causality noted on the AE form, ensures that a medically qualified assessment of causality was done. This initialed document must be retained for the required regulatory time frame. The criteria below are intended as reference guidelines to assist the investigator in assessing the likelihood of a relationship between the test drug and the adverse event based upon the available information. The following components are to be used to assess the relationship between the Merck product and the AE; the greater the correlation with the components and their respective elements (in number and/or intensity), the more likely the Merck product caused the adverse event (AE):
	
	Exposure	Is there evidence that the subject was actually exposed to the Merck product such as: reliable history, acceptable compliance assessment (pill count, diary, etc.), expected pharmacologic effect, or measurement of drug/metabolite in bodily specimen?
	Time Course	
Did the AE follow in a reasonable temporal sequence from administration of the Merck product?
 
Is the time of onset of the AE compatible with a drug-induced effect (applies to trials with investigational medicinal product)?

	Likely Cause	Is the AE not reasonably explained by another etiology such as underlying disease, other drug(s)/vaccine(s), or other host or environmental factors

Relationship	The following components are to be used to assess the relationship between the test drug and the AE:
---------------------	---

to Merck product (continued)	(continued)	
	Dechallenge	
Was the Merck product discontinued or dose/exposure/frequency reduced? If yes, did the AE resolve or improve? If yes, this is a positive dechallenge. If no, this is a negative dechallenge. (Note: This criterion is not applicable if: (1) the AE resulted in death or permanent disability; (2) the AE resolved/improved despite continuation of the Merck product; or (3) the trial is a single-dose drug trial); or (4) Merck product(s) is/are only used one time.)

	Rechallenge	
Was the subject re-exposed to the Merck product in this study? If yes, did the AE recur or worsen? If yes, this is a positive rechallenge. If no, this is a negative rechallenge. (Note: This criterion is not applicable if: (1) the initial AE resulted in death or permanent disability, or (2) the trial is a single-dose drug trial); or (3) Merck product(s) is/are used only one time). NOTE: IF A RECHALLENGE IS PLANNED FOR AN ADVERSE EVENT WHICH WAS SERIOUS AND WHICH MAY HAVE BEEN CAUSED BY THE MERCK PRODUCT, OR IF REEXPOSURE TO THE MERCK PRODUCT POSES ADDITIONAL POTENTIAL SIGNIFICANT RISK TO THE SUBJECT, THEN THE RECHALLENGE MUST BE APPROVED IN ADVANCE BY THE U.S. CLINICAL MONITOR AS PER DOSE MODIFICATION GUIDELINES IN THE PROTOCOL.

	Consistency with Trial Treatment Profile	
Is the clinical/pathological presentation of the AE consistent with previous knowledge regarding the Merck product or drug class pharmacology or toxicology?

The assessment of relationship will be reported on the case report forms /worksheets by an investigator who is a qualified physician according to his/her best clinical judgment, including consideration of the above elements.
		
Record one of the following	
Use the following scale of criteria as guidance (not all criteria must be present to be indicative of a Merck product relationship).
	
Yes, there is a reasonable possibility of Merck product relationship.	
There is evidence of exposure to the Merck product. The temporal sequence of the AE onset relative to the administration of the Merck product is reasonable. The AE is more likely explained by the Merck product than by another cause.
	

No, there is not a reasonable possibility Merck product relationship

Subject did not receive the Merck product OR temporal sequence of the AE onset relative to administration of the Merck product is not reasonable OR there is another obvious cause of the AE. (Also entered for a subject with overdose without an associated AE.)

7.2.5 Sponsor-Investigator Responsibility for Reporting Adverse Events

All Adverse Events will be reported to regulatory authorities, IRB, and investigators in accordance with all applicable global laws and regulations.

8.0 STATISTICAL ANALYSIS PLAN

8.1 Statistical Analysis Plan Summary

This is Phase I/II trial. The initial phase of the trial will use a “3+3” design. The phase II portion of the trial will use a two stage design and will not include patients treated in the phase I dose escalation for the efficacy analysis.

8.2 Statistical Analysis Plan

Phase I Design:

The primary objective of the phase I component of this study is to evaluate the safety of Pembrolizumab given in combination with Doxorubicin among patients with advanced soft tissue sarcoma. The phase I component of this study will use a 3+3 design to evaluate the 45 mg/m² and 75 mg/m² Doxorubicin dosing in combination with Pembrolizumab. Dose-limited toxicities will be evaluated through the end of the first cycle combining Pembrolizumab with Doxorubicin.

The study design is as follows:

- Initially enroll 3 patients into the 45 mg/m² cohort
 - If 2 of 3 experience a DLT, stop and conclude that Pembrolizumab may not be given safely with Doxorubicin at the protocol-specified dose levels.
 - If 1 of 3 patients experiences a DLT, enroll 3 more patients.
 - If less than 2 of 6 experiences a DLT then initiate enrollment to the 75 mg/m² cohort.
 - If 2 or more experience a DLT, stop and conclude that Pembrolizumab may not be given safely with Doxorubicin at the protocol-specified dose levels. Should this occur, discussions will initiate with the DSMB and Merck about whether the protocol could be altered to make the regimen safe or whether the study should be halted.
 - If 0 of 3 patients experience a DLT then initiate enrollment to the 75 mg/m² cohort
- If 45 mg/m² is determined safe, enroll 3 patients into the 75 mg/m² cohort
 - If 2 of 3 experience a DLT stop and conclude that the MTD is 45 mg/m²
 - If less than 2 of 3 patients experience a DLT, enroll 3 more patients.
 - If less than 2 of 6 experience a DLT then conclude 75 mg/m² is the MTD
 - If 2 or more experience a DLT, stop and conclude that that the MTD is 45 mg/m²

The maximum sample size for the phase I component is 12 patients.

Phase II Design:

The primary objective of the phase II design is to compare the objective response rate (ORR) with historical rates. Patients at the final phase I dose will not be included in the phase II analysis. Our null hypothesis estimates the overall response rate of single agent doxorubicin based on the EORTC randomized study of doxorubicin alone or in combination with Ifosfamide, the largest study using modern imaging and supportive care. A two-stage design with null hypothesis of 15% using a 1-sided 0.05 α level test has 85% power to detect an increase to 35%. This design requires a total of 35 patients, 20 in the 1st stage and 15 in the second stage. If 2 or more responses (CR or PR) are observed in the 1st stage, the study will continue accrual to the second stage, accruing 15 more patients. If at least 10 responses are seen out of the 35 patients (29%), then this will be considered evidence to rule out an ORR of 15% or less.

Secondary objectives include the estimation of the median PFS, time to and duration of response, and the frequency and severity of toxicities. With 51 patients, this design can estimate frequencies (and single time point estimates of PFS/OS) to within 14% with 95% confidence. The Kaplan-Meier method will be used to estimate median PFS and OS.

Correlative Endpoints: The study is not powered to detect specific hypotheses with regards to correlative endpoints, rather this data and analysis will help better identify patients having the potential to benefit from this therapy and aid in designing larger Phase III studies.

Summary statistics will be used to for describing changes across time. In addition, the time course of biomarker outcomes will be investigated graphically by summary plots or individual patient plots. Categorical data analysis and logistic regression will be used to evaluate the associations between correlative measures and clinical outcome (eg, response, clinical benefit, time to progression, progression-free survival, and survival). If there is suggestion of meaningful trend, methods such as linear mixed models may be used to characterize the pattern of change over time. Kaplan-Meier methodology and Cox Proportional Hazards models will be used to evaluate time to event endpoints.

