2.6 Phase II extension

[figure not shown]
The phase II extension will use a SWOG 2-stage design (modified Simon's 2 stage design) in order to detect a response rate (CR + PR) of 35%. This is based on a predicted overall response rate for single agent doxorubicin of 15%. 20 patients will be treated in the first stage. If 2 or more patients have CR or PR, an additional 15 patients will be treated. If at least 10 CR or PR's are seen, this will be considered a positive study. Patients treated in the phase I portion of the study will not be included in the phase II analysis. Any toxicity defined as a DLT for the phase I portion will also trigger a meeting of the DSMB during the phase II portion of the trial. Should 2 of these events occur, enrollment must halt until the DSMB meets.

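### The stated 85% power of the phase II two-stage rule is slightly too high: the exact power at a 35% response rate is 83.5%

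*Combined protocol and SAP*

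**What the plan says.** Section 8.2 (Phase II Design) sets the hypotheses and the level: "A two-stage design with null hypothesis of 15% using a 1-sided 0.05" level test. It then states the power: "level test has 85% power to detect an increase to 35" percent. The sample size follows as a consequence: "This design requires a total of 35 patients, 20 in the 1st stage and 15 in the second stage".

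The same paragraph gives both decision rules. At stage 1: "If 2 or more responses (CR or PR) are observed in the 1st stage, the study will continue accrual to the second stage". The final rule, in which the rate to be excluded is the 15% null or anything lower, reads: "If at least 10 responses are seen out of the 35 patients (29%), then this will be considered evidence to rule out an ORR of".

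Section 2.6 repeats the stage sizes and both thresholds and names the design family: "The phase II extension will use a SWOG 2-stage design (modified Simon's 2 stage design"). Section 5.7 says that patients not evaluable for response are replaced, so the denominators are evaluable patients. Sections 2.6 and 8.2 both exclude phase I patients from the phase II analysis.

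**The concern.** Once the stage sizes, the continuation rule, the success threshold and the two response rates are fixed, the power is also fixed. It can be computed exactly, and it does not equal the stated figure. Section 8.2 also presents the 35 patients as what the stated level and power require.

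What is at stake is modest. The power figure will be quoted when the result is interpreted, above all if the count falls just below the threshold (9 of 35, for example). A reader relying on the plan would take the chance of missing a truly 35% active regimen to be 15%, when it is 16.5%.

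**Working it through.** **Inputs**

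- Null response rate 15%, alternative 35%, 1-sided level 0.05 (section 8.2).
- Stage 1: 20 patients, continue on 2 or more responses. Stage 2: 15 patients. Positive on 10 or more of 35 (sections 2.6 and 8.2).
- Non-evaluable patients replaced (section 5.7), so no allowance for dropout.

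**Formula**

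Let X1 ~ Bin(20, p) be the stage 1 responses and X2 ~ Bin(15, p) the stage 2 responses. The probability of a positive trial is

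P(p) = Σ over x = 2 to 20 of P(X1 = x) × P(X2 ≥ 10 − x).

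**Power, p = 0.35**

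| x | P(X1 = x) | P(X2 ≥ 10 − x) | product |
|---|---|---|---|
| 2 | 0.00998 | 0.11323 | 0.00113 |
| 3 | 0.03226 | 0.24516 | 0.00791 |
| 4 | 0.07382 | 0.43572 | 0.03217 |
| 5 | 0.12720 | 0.64806 | 0.08243 |
| 6 | 0.17123 | 0.82730 | 0.14166 |
| 7 | 0.18440 | 0.93827 | 0.17302 |
| 8 | 0.16135 | 0.98582 | 0.15906 |
| 9 | 0.11584 | 0.99844 | 0.11566 |
| 10 or more | 0.12178 | 1 | 0.12178 |

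The products sum to **0.8348**. The plan states 0.85. The difference is 0.85 − 0.8348 = 0.0152, and the false-negative risk is 1 − 0.8348 = 0.1652.

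**Does the stage 1 look explain the gap?** No. At a 35% rate, the chance of stopping with 0 or 1 response in 20 is 0.2%. A single-stage rule of 10 or more of 35 has power 0.8349, so the loss from the interim look is 0.0001.

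**Do common approximations give 85%?**

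- One-sample normal approximation, N = 35, 1-sided 0.05: Φ{[√35 × 0.20 − 1.645 × √(0.15 × 0.85)] / √(0.35 × 0.65)} = 89.4%.
- The same formula at 1-sided 0.029, the level actually attained: 85.6%.
- Arcsine approximation at 1-sided 0.05: 87.3%.

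None is exactly 85%, and the document does not say how its figure was obtained.

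**Type I error, p = 0.15**

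- The same sum gives 0.0292, below the 0.05 ceiling.
- With 9 of 35 as the threshold it would be 0.0688, above the ceiling. With 11 of 35 it would be 0.0110, and power would fall to 72.8%.
- So 10 is the smallest threshold at 35 patients that keeps a 1-sided 0.05 level.

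**How far off is 85%?** The rule reaches 85% power at a true response rate of 35.5%.

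**Neighbouring sample sizes** (stage 1 rule unchanged, smallest threshold with type I error at or below 0.05):

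| N | threshold | type I error | power at 35% |
|---|---|---|---|
| 32 | 9 | 4.1% | 84.2% |
| 33 | 9 | 4.9% | 86.8% |
| 34 | 10 | 2.4% | 80.4% |
| 35 | 10 | 2.9% | 83.5% |
| 36 | 10 | 3.5% | 86.1% |

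Exact power moves up and down with N because the threshold must be a whole number. At 35 it falls just short of the stated figure.

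**The case against.** The best defence is that 85% is a whole-number planning figure and the shortfall is only 1.5 points. The 15% and 35% are themselves round planning values, and moving the alternative by half a point restores 85%. No decision turns on the difference: the stage 1 rule and success threshold in sections 2.6 and 8.2 agree with each other and are workable. All of that stands, and it is why the point is minor. It does not make the sentence correct: 83.5% is not 85% to the nearest whole percent, the figure errs in the favourable direction, and the documents attach no tolerance to it.

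Two stronger readings are tempting, and neither is supported.

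- A reader might infer that the 0.05 is also misstated, because the exact type I error is 2.9%. Section 8.2 describes a test at the 0.05 level. A level is a ceiling, and 2.9% respects it. A binomial count cannot in general be cut to give exactly 5%, and 9 of 35 would break the ceiling at 6.9%. The plan nowhere says that the attained error is 5%.
- A reader might infer that the sample size should change, since 20 + 13 patients with 9 or more responses satisfies both 0.05 and 85%. That design has almost no margin: if the true null rate were 15.5%, its type I error would be 5.9%, against 3.6% for the plan's rule. The null is a historical estimate, so a conservative rule is a reasonable choice. A different N that meets both targets does not make the chosen design wrong.

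**Conclusion.** The point holds as a small overstatement of power for the phase II primary endpoint: 83.5% exact against 85% stated, or a false-negative risk of 16.5% against 15%. The level claim is sound, and 10 of 35 is the right threshold for it. The severity is low, because no conclusion that the rule can produce is invalidated.

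The result assumes independent responses with a common rate, exactly 20 and then 15 evaluable patients, and the decision rules as written. It needs no figure from outside the documents.

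**What to change.** In section 8.2, replace the 85% with the exact value, for example: the two-stage rule has an exact power of 83.5% at a true response rate of 35%. Optionally add that its exact one-sided type I error at a 15% rate is 2.9%, so that a positive result can be read at the level actually attained. The next sentence, on the 35 patients required, should then refer to the design as specified and no longer to an 85% target.

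Leave the 20 + 15 sample size, the stage 1 rule and the success threshold unchanged. Section 2.6 quotes no power and needs no edit. The cost is a wording change in one paragraph and a slightly less favourable stated power, with no extra patients.

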1.1 TRIAL SUMMARY

Abbreviated Title	Pembrolizumab and Doxorubicin
Trial Phase	Phase I/II
Clinical Indication	Sarcoma
Trial Type	Single arm, open-label
Type of control	Historical
Route of administration	IV
Trial Blinding	None
Treatment Groups	Low and high dose doxorubicin/ phase I and phase II expansion
Number of trial subjects	maximum 47 (44 expected)
Estimated enrollment period	24 months
Estimated duration of trial	48 months
Duration of Participation	48 months

1.2 Table of contents:

1. Title

- 1.1 Trial Summary
- 1.2 Table of contents
- 1.3 Commonly Used Abbreviations

2. Trial Design

- 2.1 Introduction
- 2.2 Dosing Schedule
- 2.3 Management of Normal Doxorubicin Toxicity
- 2.4 Assessment of Response
- 2.5 Phase I Dose Escalation
- 2.6 Phase II Extension
- 2.7 Trial Diagram

3. Objectives

- 3.1 Primary Objectives and Hypothesis
- 3.2 Secondary Objectives and Hypothesis
- 3.3 Exploratory Objectives

4. Background and Rationale

- 4.1 Background
- 4.2 Rationale

5. Methodology

- 5.1 Entry Criteria
- 5.2 Trial Treatments
- 5.3 Concomitant Medications/Vaccinations (allowed & prohibited)

- 5.4 Rescue Medications & Supportive Care related to Pembrolizumab
- 5.5 Diet/Activity/Other Considerations
- 5.6 Subject Withdrawal/Discontinuation Criteria
- 5.7 Subject Replacement Strategy
- 5.8 Criteria for Early Trial Termination

- 6. Trial Flow Chart

- 7. Trial Procedures
 - 7.1 Trial Procedures
 - 7.2 Assessing and Recording Adverse Events
 - 7.3 Analysis of Biopsy Specimen

- 8. Statistical Analysis and Plan
 - 8.1 Statistical Analysis and Plan Summary
 - 8.2 Statistical Analysis Plan

- 9. Labeling, Packaging, Storage and Return of Clinical Supplies
 - 9.1 Investigational Product
 - 9.2 Packaging and Labeling Information
 - 9.3 Clinical Supplies Disclosure
 - 9.4 Storage and Handling Responsibilities
 - 9.5 Returns and Reconciliation

- 10. Administrative and Regulatory Details
 - 10.1 Institutional Review Board
 - 10.2 Consent
 - 10.3 Termination of Study
 - 10.4 Compliance with Trial Registration and Results Posting Requirements

10.5 Response Evaluation Criteria in Solid Tumors (RECIST) 1.1 Criteria for Evaluating Response in Solid Tumors

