2.0 TRIAL DESIGN

2.1 Introduction

This is a Phase I/II, non-randomized, open-label, interventional study of Pembrolizumab combined with doxorubicin for patients with advanced sarcoma. Most patients will receive this as front line therapy. As a rule, the trial is generally inclusive for most sarcoma subtypes. However, it excludes patients with prior anthracycline treatment. Patients with Ewings Sarcoma, Osteosarcoma, and some Rhabdomyosarcomas are excluded as these histologic sarcoma subtypes have well-established, evidence-based treatment paradigms combining anthracyclines with other chemotherapy.

The Phase I stage will evaluate two dose levels of doxorubicin (45 and 75 mg/m²) combined with Pembrolizumab. The 75 mg/m² doxorubicin dose is widely considered standard of care for sarcoma, as is being used as the “control” arm for recent and on-going phase III trials (NCT02451943) (Judson, Verweij et al. 2014). All patients will receive Pembrolizumab at the flat dose of 200 mg given intravenously every 3 weeks. Unless serious adverse events are observed, the Phase II expansion will combine the 75 mg/m² dose of doxorubicin with Pembrolizumab.

The phase II portion will use a two stage design treating an initial 20 patients with the combination of Doxorubicin and Pembrolizumab. If two or more objective responses are seen (either complete or partial responses), an additional 15 patients will be treated for a total of 35 patients. In summary, we expect that 44 patients will be treated on the trial (9 in the phase I portion and 35 on the phase II portion). If an additional 3 patients needed to be treated in the initial phase I cohort this could potentially increase to a maximum enrollment of 47.

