2.4 Assessment of Response

Response assessment will be based on RECIST 1.1. Patients with clinical benefit (SD, PR, CR) after 6 cycles of doxorubicin will continue on single agent Pembrolizumab until confirmed progression RECIST, severe toxicity (see **Section 5**), or 2 years of therapy whichever comes first. Patients who receive a CR will be treated until they have had at least 24 weeks of treatment and have been treated for at least 2 cycles after their CR was declared. Patients who are able to be brought to a CR surgically should be treated just as if they had a CR in response to the medication. Patients confirmed to have a CR who have been taken off treatment will continued to be monitored radiographically every 12 weeks. Upon relapse they can be re-treated with Pembrolizumab for up to one year.

While, all patients will start therapy with unresectable/metastatic disease, it is possible that a responding patient becomes surgically resectable so that they have no evidence of disease. These patients may undergo surgery and afterwards should be followed as if they had a CR, with the rules regarding progression and restarting treatment.

Patients will have their first post-treatment scan after 3 cycles of doxorubicin, prior to receiving their fourth cycle of doxorubicin. Patients with PR or SD will have their second post treatment scan 3-6 weeks after their last (sixth) cycle of doxorubicin. Responses will be determined by RECIST 1.1. After 6 cycles of doxorubicin have been completed and Pembrolizumab is being given as a single agent, scans will be performed every 12 weeks (+/- 1 week) until progression.

Subjects with an *unconfirmed* progression of disease may discontinue but will be encouraged to continue trial treatment until progression is confirmed following two additional cycles of therapy or until disease progression becomes symptomatic. However, subjects may only receive study treatment while waiting for confirmation of PD if the following criteria are met:

- No decline in ECOG performance status
- Absence of rapid progression of disease
- Absence of progressive tumor at critical anatomical sites (e.g. cord compression) requiring urgent alternative medical intervention

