5.7 Subject Replacement Strategy

The phase II expansion dose will treat up to 35 patients evaluable for response to therapy (20 in the first stage, then if at least 2 responses are seen, an additional 15 patients). If patients become ineligible prior to starting therapy or for some other reason fail to be evaluable for response assessment, additional patients will be treated in their place.

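### Is the stage-1 rule (continue with 2 or more responses in 20) too lenient to protect against a combination no better than doxorubicin alone?

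*Combined protocol and SAP*

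**What the plan says.** The stage-1 rule appears in four places, with the same numbers each time.

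- Section 8.2: "If 2 or more responses (CR or PR) are observed in the 1st stage, the study will continue accrual to the second stage".
- Section 2.6: "If 2 or more patients have CR or PR, an additional 15 patients will be treated".
- Section 2.1: "If two or more objective responses are seen (either complete or partial responses), an additional 15 patients will be treated".
- Section 5.7: "20 in the first stage, then if at least 2 responses are seen, an additional 15 patients".

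Section 8.2 gives the error rates: "A two-stage design with null hypothesis of 15% using a 1-sided 0.05" level test, with 85% power at a response rate of 35%. The trial is positive with at least 10 responses in 35. Phase I patients are excluded from this analysis, and section 5.7 replaces patients who cannot be evaluated, so 20 and 35 are evaluable counts.

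On timing, section 2.4 says "Patients will have their first post-treatment scan after 3 cycles of doxorubicin, prior to receiving their fourth cycle of doxorubicin" and "Patients with PR or SD will have their second post treatment scan 3-6 weeks after their last (sixth) cycle of doxorubicin". After doxorubicin, scans continue every 12 weeks until progression. No probability of early stopping is stated or required anywhere.

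**The concern.** Two responses in 20 is an observed rate of 10%, below the 15% the combination must beat. From that point the trial needs 8 responses in the remaining 15, which is very unlikely. Under the null the rule lets about 82% of trials go on to stage 2. A cutoff of 3 would stop more than twice as many null trials and, on a simple calculation, would cost almost no power. The sections that state the rule also do not say when stage-1 responses are counted, although the first scan comes about 12 weeks after a patient starts.

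At stake are up to 15 further patients who would receive added pembrolizumab in a trial unlikely to meet its response criterion.

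**Working it through.** **Inputs.** Null 15%, alternative 35%, one-sided 0.05, stages of 20 and 15, continue at 2 or more, success at 10 or more of 35 (all section 8.2). Let X1 ~ Bin(20, p) and X2 ~ Bin(15, p), and let c be the continuation cutoff.

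P(stop) = P(X1 < c). P(success) = Σ over x ≥ c of P(X1 = x) · P(X2 ≥ 10 − x). Expected N = 20 + 15 · (1 − P(stop)).

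**The plan's own design, c = 2.**

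- Power at 35%: 83.5%, against a stated 85%.
- Type I error at 15%: 2.9%. A final cutoff of 9 would give 6.9%, so 10 is the smallest final cutoff that holds 5%.
- P(stop): 73.6% at a true rate of 5%, 39.2% at 10%, 17.6% at 15%, 0.2% at 35%.
- Expected N at 15%: 20 + 15 · 0.8244 = 32.4.

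The look therefore guards mainly against a combination worse than doxorubicin alone, and the design as a whole meets its alpha.

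**The alternative, c = 3, all 20 fully assessed.**

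| | c = 2 | c = 3 |
|---|---|---|
| Type I error | 2.9% | 2.9% |
| Power at 35% | 83.5% | 83.4% |
| P(stop) at 15% | 17.6% | 40.5% |
| P(stop) at 20% | 6.9% | 20.6% |
| P(stop) at 25% | 2.4% | 9.1% |
| P(stop) at 35% | 0.2% | 1.2% |
| Expected N at 15% | 32.4 | 28.9 |

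Only the outcome X1 = 2 is treated differently. Its probability is 22.9% at 15% and 1.0% at 35%. From there success needs 8 of 15, with probability 0.06% at 15% and 11.3% at 35%. The power lost is 0.0100 · 0.113 = 0.0011, or 0.1 point. The mean saving at 15% is 15 · 0.2293 = 3.4 patients.

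**What the 0.1 point depends on.** It requires every response that counts at the end to be visible at the look. Cycle 1 is pembrolizumab alone, so the fourth doxorubicin dose falls at week 12 and the sixth at week 18. The second scan is then at weeks 21 to 24. Scanning continues every 12 weeks afterwards, and nothing closes the response count at the second scan. Suppose each eventual stage-1 responder is visible at the look with probability v (an assumption), and the final count uses all responses:

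| v | Power, c = 2 | Power, c = 3 | Loss (points) | P(stop) at 35%, c = 2 | P(stop) at 35%, c = 3 |
|---|---|---|---|---|---|
| 100% | 83.5% | 83.4% | 0.1 | 0.2% | 1.2% |
| 90% | 83.4% | 82.9% | 0.5 | 0.5% | 2.6% |
| 80% | 83.2% | 81.6% | 1.6 | 1.2% | 5.3% |
| 70% | 82.5% | 78.6% | 3.8 | 2.7% | 10.0% |

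**Accrual pause.** The trial summary gives "maximum 47 (44 expected") patients and 24 months of enrolment. That is 44/24 = 1.83 a month, assuming an even rate. About 5 patients then enrol in 12 weeks and 9 to 10 in 21 to 24 weeks. When patient 20 starts, roughly 15 of the 20 have had a first scan and 10 a second. The chance that the cutoff has not yet been reached, so that accrual would have to wait, is P(Bin(n, p) < c) with n from 15 down to 10:

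- At 35%: 1% to 9% with c = 2, and 6% to 26% with c = 3.
- At 15%: 32% to 54% with c = 2, and 60% to 82% with c = 3.

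The wait could last up to about 24 weeks. Without a wait, patients already enrolled cut the saving to (15 − 5.1) · 0.2293 = 2.3 patients if the decision is made at patient 20's first scan. At the second scan it is 1.1 to 1.4.

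**The case for a change.** The best case for the change is that exactly 2 of 20 is nearly a lost position even at 35%, that the null is the case in which pembrolizumab adds no response benefit, and that one number in four places would more than double the stopping probability there without raising alpha. Stating when stage-1 responses are counted would help under either cutoff.

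The arithmetic stands in full. A sponsor who put most weight on stopping at the null could reasonably have chosen 3. But preferring 3 to 2, or 3 to 4, needs a threshold for acceptable power loss, and the documents give none. The costs also go beyond the 0.1 point: a more frequent accrual pause, more stopping at true rates of 20% and 25%, and fewer patients for safety, which section 3.1.1 lists as a primary objective. For a frequency near 50%, the 95% half-width 1.96 · √(0.25/n) is about 22 points with 20 patients and 17 with 35.

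A lenient look also suits a mixed population. Section 4.2.1 reports 5 responses in 40 patients in one checkpoint-inhibitor study, 4 of them in a single subtype, and none in 12 uterine leiomyosarcomas. The subtype mix of the first 20 patients could decide between 2 and 3 responses.

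On timing, section 8.2 already makes stage-2 accrual depend on responses having been observed in stage 1. The exact counting date is a missing operational detail, not a contradiction or a flaw in the rule.

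**Conclusion.** The concern does not hold. The rule is consistent across sections 2.1, 2.6, 5.7 and 8.2, keeps the type I error at 2.9% against a 5% limit, has 83.5% power against a stated 85%, and misses no target the documents set. Its 17.6% stopping probability at the null is low, but it follows from a permissible choice to use the look mainly against a combination worse than doxorubicin alone. The alternative saves at most 3.4 patients on average at the null. It costs 0.1 point of power if all responses are visible at the look and 0.5 to 3.8 points if 90% to 70% are, and stopping at a true 25% rises from 2.4% to 9.1%. These figures rest on exact binomial calculation with 20 and 35 evaluable patients. The visibility range and the even accrual rate are assumptions, but the error rates and stopping probabilities of the plan's own rule with all 20 assessed depend on neither.
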